3.1.4.2 Deaths

The deaths observation period are per the observation periods defined below.

- Deaths from first IMP injection until CSED:
 - Treatment-emergent deaths: deaths occurring during the TEAE period
 - Post-treatment emergent deaths
- Deaths post-CSED

3.1.4.3 Laboratory safety variables

Clinical laboratory data consists of blood analysis, including hematology, clinical chemistry, and urinalysis. Clinical laboratory values after conversion will be analyzed into standard international units. International units will be used in all listings and tables. Clinical laboratory values converted into conventional (US) units will be also available in the database. Analyses can be provided upon request.

Blood samples for clinical laboratories will be taken as described in the study flow chart in the protocol.

The laboratory parameters will be classified as follows:

- Hematology
 - **Red blood cells and platelets**: hemoglobin, hematocrit, red blood cell count, platelet count;
 - White blood cells: white blood cell count, neutrophils, lymphocytes, monocytes, basophils, eosinophils.

- Clinical chemistry
 - **Metabolism:** fasting plasma glucose, total protein, albumin, creatine phosphokinase (CPK);
 - Electrolytes: sodium, potassium, chloride, calcium, phosphorus, bicarbonate;
 - Renal function: creatinine, eGFR, blood urea nitrogen, uric acid;
 - Liver function: alanine aminotransferase (ALT), aspartate aminotransferase (AST), alkaline phosphatase (ALP), gamma glutamyl transferase (γGT), lactate hydrogenase (LDH), total bilirubin, and in case of total bilirubin values above the normal range, must include direct and indirect bilirubin (used for describing individual cases only);
 - Hepatitis screen: anti-hepatitis-C antibody.

Technical formulas are described in Section 3.5.1.

3.1.4.4 Vital signs variables

Vital signs include: weight, heart rate, systolic and diastolic blood pressure in sitting position.

3.1.4.5 Electrocardiogram variables

Electrocardiograms were recorded automatically by the device at the Investigator site.

Electrocardiogram assessments will be described as normal or abnormal.

3.1.5 Other endpoints

Other assessment endpoints defined below are exploratory.

3.1.5.1 Lipid parameters

The lipid parameters include values (in conventional [US] and international units), percent change from baseline, and/or when appropriate absolute change from baseline (in conventional and international units) over time for the following parameters: LDL-C, TC, HDL-C, fasting TGs, non-HDL-C, Apo A-1, Apo B, ratio Apo B/Apo A-1, Lp (a), ratio TC/HDL.

All these parameters are measured or calculated by a central laboratory, for both scheduled and unscheduled time points. For LDL-C analysis, both calculated and measured LDL-C values will be taken into account. In case both calculated and measured LDL-C are provided for the same sampling, the measured LDL-C will be considered. Calculated LDL-C is obtained using the Friedewald formula. Non-HDL-C is calculated by subtracting HDL-C from the TC.

Unless otherwise specified, all central measurements (scheduled or unscheduled, fasting or not fasting) may be used to provide a value for each timepoint, even if assessed after treatment discontinuation (intent-to-treat [ITT] approach). The analysis windows used to allocate a measurement to a time point are defined in Section 3.5.4. For TG, only fasting measurements will be used. Measurements with missing fasting status will be excluded from the analyses.

For all time points post-baseline, the value used for the analyses at a given time point (eg, at Month 24) is the value obtained within the corresponding analysis window. The baseline value is the last available measurement obtained up to the date and time of the first double-blind IMP injection. For patients randomized and not treated, the baseline value is defined as the last available value obtained up to the date and time of randomization.

Percent changes from baseline to a timepoint are defined as: 100 x (parameter value at the time point – parameter value at baseline) / parameter value at baseline.

Data handling conventions for other endpoints are described in Section 3.5.

3.1.5.2 hs-CRP

The percent change in hs-CRP from baseline over time is defined using same definitions and rules as for LDL-C, when applicable (see section above). hs-CRP values greater or equal to 10 mg/L will be excluded from analyses in a second approach, since these are suggestive of concurrent infections, MI, or other events provoking an acute phase response (2).

PCSA criteria for hs-CRP are defined in Appendix A.

3.1.5.3 HbA_{1C}

The absolute change in HbA_{1c} (%) from baseline over time: same definitions and rules as for LDL-C (see Section 3.1.5.1).

3.1.5.4 Patients with LDL-C <25 mg/dL (0.65 mmol/L)

The assessment will include:

- The proportion of patients with two consecutive results, spaced out by at least 21 days, of LDL-C <25 mg/dL (<0.65 mmol/L) (respectively LDL-C <15 mg/dL, ie, <0.39 mmol/L) during the double-blind treatment period
- The time to the first LDL-C <25 mg/dL (respectively LDL-C <15 mg/dL) for these patients.

In case both calculated and measured LDL-C are provided for the same sampling, the measured LDL-C will be considered.

3.1.5.5 Anti-alirocumab antibodies assessed throughout the study.

Anti-alirocumab antibodies (ADAs) are assessed at Visit 3 (Month 0), Visit 5 (Month 2), Visit 6 (Month 4), and Visit 10 (Month 12) for the first year, then every year and at the final on-treatment visit (CSED visit for completers, or early end of treatment visit for patients who discontinued the treatment).

ADA measurements will be assigned to analysis windows as defined in Section 3.5.4.

The following variables will be described:

- ADA response (Positive or Negative). For ADA positive:
 - Titer levels
 - Neutralizing status (Positive or Negative)
- Pre-existing positive ADA defined as patients with positive ADA response at baseline with less than 4-fold increase in titer in the post-baseline period
- Treatment-emergent positive ADA response defined as 1) Patients with no ADA positive response at baseline but with any positive response in the post-baseline period (up to follow-up visit) or 2) Patients with a positive ADA response at baseline and at least a 4-fold increase in titer in the post-baseline period (up to follow-up visit). For treatment-emergent positive ADA, the following categories for ADA duration will be applied:
 - A persistent positive response is a treatment-emergent ADA positive response detected in at least 2 consecutive post-baseline samples separated by at least a 16-week period
 - An indeterminate duration positive response is defined as ADA present only at the last sampling time point
 - A transient positive response is defined as any treatment-emergent positive ADA response that is neither considered persistent nor indeterminate

In addition, potential ADA samples that are to be collected after CSED visit for patients with titer \geq 240 at CSED visit will be listed.

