### 10.3.4 Handling of patients after permanent treatment discontinuation

Patients in whom IMP treatment discontinuation is considered permanent by Investigator should come for an extra visit (early end-of-treatment visit V70) as soon as practically possible (within 1 month) after IMP discontinuation is considered permanent by Investigator. V70 is similar to the common end of study visit (Visit 30, Month 64) for study treatment completers, and should include similar procedures.

Such patients must continue to remain in the study and will be strongly encouraged to complete all the remaining study visits as originally scheduled in [Section 1.2](#), until the common study end-date visit. Therefore, a contact should be maintained with these patients every 2 to 3 months (as per study assessments), and a clinic visit performed every 4 to 6 months until the common study end-date visit (V30).

- Over the 6 months following V70, all assessments (other than IMP administration and its associated procedures) should be performed as originally planned. These include but are not limited to collection of suspected efficacy endpoints, AE/AESI/SAE, concomitant medications, hematology and chemistry labs, lipid labs and anti- alirocumab antibodies.
- From 6 months post V70 until common study end date visit (V30), assessment at visits are simplified and will include updating patient contact information (as well as patients' family and patient's GP/cardiologist) and the collection of:
  - suspected efficacy endpoints
  - cardiovascular events of interest other than efficacy endpoints (peripheral arterial disease and venous thromboembolic events)
  - related and/or serious AEs
  - selected concomitant medications (statins, ezetimibe)
  - selected labs:
    - anti alirocumab antibodies, lipid panel and HbA1c: annually (at M12, M24, M36, M48, M60) and at common study end-date
    - ApoB at month 24 and at common study end-date.

Previously observed AEs/AESIs/SAEs that had not resolved should be followed-up until an outcome (e.g. resolution, stabilization) has been determined.

- In case of difficulty to comply with the 4 to 6-month clinic visit periodicity in patients who discontinued treatment early, every effort should be made to have an actual clinic visit at least annually (with periodic phone/internet contacts every 3 months in between) and a final visit V30. During that annual visit and at V30, selected blood samples as described above should be collected.

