The time to the first TEAE/event will be compared for patients with 2 consecutive LDL-C <25 mg/dL versus $\geq 25 \text{ mg/dL}$, within the alirocumab group, using a Cox model, including the covariate for 2 consecutive LDL C <25 mg/dL (Yes/No). Hazard ratio (and 95% CI) from this model will be provided. The event rate per 100 patient-years (the number of patients with an event in question divided by total 100 patient-years) will also be provided.

Second screening approach

TEAE summary by primary SOC, HLGT, HLT, and PT as well as groupings of events (ie, cataract, neurological events, neurocognitive disorders and "new onset of diabetes" will be provided on the safety population according to baseline LDL-C categories (eg, <70, ≥70 to <90, ≥90 to <110, ≥110 mg/dL).

Hazard ratio (and 95% CI) for alirocumab effect versus placebo within each baseline LDL-C subgroup will be provided using a Cox model with baseline LDL-C (in categories), treatment group and the treatment-by-baseline LDL-C interaction term.

To assess the impact of baseline LDL-C on hazard ratio, a Cox model including the baseline LDL-C (as continuous factor), treatment group and treatment-by-baseline LDL-C interaction term will be used. The p-value from the interaction term will be provided for descriptive purpose to evaluate if there is a potential relationship between baseline LDL-C and hazard ratio.

Second step

For each pre-specified event (cataract, neurological events, neurocognitive disorders, new onset of diabetes) as well as for each event with a potential signal detected in the first step, the time to the first TEAE/event will be compared for patients with 2 consecutive LDL-C <25 mg/dL versus \geq 25 mg/dL, within the alirocumab group, using a Cox model, including the covariate for 2 consecutive LDL-C <25 mg/dL (Yes/No) and prognostic factors of the event analyzed. Adjusted HR (and 95% CI) from this model will be provided.

The list of prognostic factors will be established based on the literature and on study data (as applicable).

Subgroups of patients with treatment-emergent ADA positive response

All TEAEs by primary SOC, HLGT, HLT, and PT as well as local injection site reactions will be described in the alirocumab group according to the following ADA parameters:

- Treatment-emergent ADA positive response (yes/no)
- Persistent/transient/indeterminate treatment-emergent ADA positive response.

Analysis of all treatment-emergent serious adverse event(s)

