3.4.7.5 Analyses of anti-alirocumab antibody variables

The following summaries will be performed on the ADA population, taking into account all samples regardless of timing in relation to injections. ADA results will be summarized by treatment group and up-titration status (see Section 3.4.5).

- ADA results (negative or positive) by time point;
- Neutralizing status (negative or positive) by time point for positive ADA;
- ADA titers using descriptive statistics (median, minimum, and maximum) for positive ADA by time point;
- Number (%) of patients with pre-existing ADA and number (%) of patients with treatment-emergent ADA positive response;
- Number (%) of patients with persistent/transient/indeterminate treatment-emergent ADA positive response;
- Time to onset of treatment-emergent ADA positive response using descriptive statistics;

- 11-Oct-2017 Version number: 3
- Number (%) of patients with at least 1 neutralizing ADA.

Correlations between ADA parameters (eg, titers, treatment-emergent ADA positive status, neutralizing status), safety and/or efficacy endpoints will be also explored (eg, scatter plot).

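### The SAP's ADA duration rule can label a response transient while it is still positive at the last sample, although a single positive at that sample counts as indeterminate

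*SAP*

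**What the plan says.** SAP 3.1.5.5 defines three duration classes for a treatment-emergent ADA response.

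- Persistent: positivity "detected in at least 2 consecutive post-baseline samples separated by at least a 16-week period".
- Indeterminate: "An indeterminate duration positive response is defined as ADA present only at the last sampling time point".
- Transient: "A transient positive response is defined as any treatment-emergent positive ADA response that is neither considered persistent nor indeterminate".

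After baseline, samples are taken at Months 2, 4 and 12 "for the first year, then every year and at the final on-treatment visit". After permanent treatment discontinuation, Protocol 10.3.4 continues sampling "annually (at M12, M24, M36, M48, M60) and at common study end-date". Protocol 6.2.2 makes the common study end date (CSED) one calendar date for everyone, and Protocol 10.1.5.4 places the final visit 0 to 30 days after it. A further sample 6 to 12 months later is planned only for titers of 240 or more at the end (Protocol 9.3.1.1). SAP 3.1.5.5 lists it and gives it no part in the classification.

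The classes are used twice. SAP 3.4.7.5 tabulates the "Number (%) of patients with persistent/transient/indeterminate treatment-emergent ADA positive response". SAP 3.4.5.1 describes adverse events and local injection site reactions in the alirocumab group by the same split.

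**The concern.** Transient implies that the response went away, yet the SAP makes it the residual class and does not ask for a negative sample. A response with two closely spaced final positives fails the persistent rule because the span is too short. It fails the indeterminate rule because there is more than one positive, so it falls into transient. A patient with an isolated early positive, later negatives and a new positive at the last sample also lands there, with the latest episode still open.

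The ordering is perverse. One final positive leaves the duration open, but adding a second positive just before it changes the label to transient.

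Evaluating ADA development is a stated secondary objective (SAP 1.2.2). The rule places unresolved responses with resolved ones in the ADA table and in the safety description by ADA class.

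**Working it through.** **1. The rule applied to sample patterns** (a month is 30.4375 days; 16 weeks is 112 days).

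| Post-baseline samples | Last interval | SAP label |
|---|---|---|
| Negative to Month 12; positive at Month 24 and at a final visit at Month 26 | 61 days | transient |
| Negative to Month 24; positive at Month 26 only | 61 days | indeterminate |
| Positive at Month 2; negative at Months 4 to 24; positive at Month 26 | 61 days | transient |
| Positive at Months 4 and 12; negative at Month 24; positive at Month 26 | 61 days | persistent |
| Negative to Month 12; positive at Month 24 and at a final visit at Month 30 | 183 days | persistent |

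Rows 1 and 3 are the defect. Rows 2, 4 and 5 mark its limits.

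**2. Accrual (SAP Table 1, Protocol Table 3).** The monthly rates sum to 2004 by Month 11 and 2564 by Month 12. By Month 40 they give 2564 + 28 × 560 = 18,244, against the stated 18,000 (1.4% higher).

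**3. How often the last interval is short.** Take the CSED at Month 64, the final visit on that date, and entry spread evenly within months. The 29 months at 560 per month have follow-up from 24 to 53 months. The last interval is short when follow-up T lies within 112/30.4375 = 3.68 months after Month 24, 36 or 48: 3 × 3.68 × 560 = 6182 patients. Earlier entrants within 3.68 months after Month 60 add 0.68 × 32 + 32 + 32 + 64 = 150. Together, 6332/18,244 = 35%.

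With the final visit 0 to 30 days after the CSED, simulation of 1,000,000 patients gives 33%. It gives 30% if an annual sample within 14 days of the final one is merged with it, and 26% if within 28 days. Without the accrual detail, 112/365.25 = 31%.

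**4. How often the label is wrong.** Take durable responders, who turn positive once and stay positive, with all planned samples obtained. The mislabel also needs onset in the 12 months before the penultimate sample. The documents give no onset distribution, so it is varied.

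- *Onset uniform over follow-up:* the chance is 12/T. Integrating over the three short bands gives 560 × 12 × [ln(27.68/24) + ln(39.68/36) + ln(51.68/48)] = 6720 × 0.3138 = 2109. The early entrants add about 150 × 12/62 = 29. The share is 2138/18,244 = 11.7%.
- *The same, with samples under 28 days apart merged:* 6720 × [ln(27.68/24.92) + ln(39.68/36.92) + ln(51.68/48.92)] = 6720 × 0.2320 = 1559, plus about 18. The share is 1577/18,244 = 8.6%.
- *Exponential onset, mean 3 months:* only the first band matters. The share is (3.68 × 560/18,244) × (e⁻⁴ − e⁻⁸) = 0.113 × 0.018 = 0.2%.
- *Exponential onset with longer means (simulation, final visit 0 to 30 days after the CSED, merging 0 to 28 days):* 1.2% to 1.4% for a mean of 6 months, 3.1% to 3.8% for 12 months, 5.0% to 6.2% for 24 months.

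**The case against.** Two stronger readings are tempting, and the documents support neither. The first is that every final positive run under 16 weeks becomes transient. Rows 2 and 4 of the table show otherwise; with uniform onset, 54% to 64% of short final runs in durable responders are a lone final positive and therefore indeterminate. The second is that 26% to 35% is the mislabelling rate. It is the share of patients with a short last interval, and the mislabel also needs onset just before the penultimate sample.

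It is also tempting to add patients positive at Months 2 and 4 only, or at a scheduled visit and again at the early end-of-treatment visit. These would be mislabelled only if no later sample exists, and Protocol 8.3.3, 9.3.1.1 and 10.3.4 plan sampling after discontinuation. They arise only through death, withdrawal or missed visits.

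SAP 3.1.5.5 assigns ADA values to analysis windows, and SAP 3.5.4 keeps one value per window. That could absorb some closely spaced samples and turn those patients indeterminate. But SAP 3.4.7.5 takes all samples into account, so the text does not settle which governs the duration class. Merging samples up to 28 days apart reduces the effect without removing it.

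Finally, the label feeds no hypothesis test. ADA status, titers, neutralizing status, treatment-emergent counts and time to onset do not depend on it. That stands, and it limits the weight of the point.

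**Conclusion.** The rule gives a wrong label for a definable set of patients: still positive at the last sample, no persistent run, and more than one positive sample. This follows from the definitions alone, and no other SAP section corrects it.

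The size is modest: roughly 0.2% to 12% of durable responders. That range rests on the planned accrual, a CSED at Month 64, complete sampling and an assumed onset time. Early onset puts it near the bottom, and onset spread evenly over follow-up near the top. It covers durable responders only; relapsing patterns such as row 3 are not quantified. No patient count can be given, because the documents state no ADA incidence.

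A reader might infer that the immunogenicity or safety conclusions are materially biased. The documents do not show that. The classification is descriptive and does not affect the primary analysis. It is still worth correcting, because it concerns a stated objective and the change costs almost nothing.

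**What to change.** In SAP 3.1.5.5, apply the classes in order to each treatment-emergent response:

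1. Persistent, as now defined.
2. Otherwise indeterminate, if ADA is positive at the last available sample up to and including the CSED visit.
3. Otherwise transient, meaning that the last available sample is ADA-negative.

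The order keeps the classes from overlapping, including for the early-isolated-positive pattern. State that the derivation uses all actual sample dates, not windowed values. Keep the post-CSED sample as a separate listing: it is taken only at titers of 240 or more, so using it would make follow-up for classification depend on titer.

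The cost is a few sentences and one derivation, with no new samples. The persistent count is unchanged. Some responses move from transient to indeterminate, and no response still positive at the last sample remains transient. In the 14-day-merge scenario with uniform onset, indeterminate rises from 14.2% to 24.3% of durable responders and persistent stays at 75.7%. With a mean onset of 6 months it rises from 0.5% to 1.8%. The downside is a larger class with no resolved duration, which is what the data can support.

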3.1.5.6 Quality-of-life parameters

EQ-5DTM is a standardized and generic instrument for measuring the health status and health related quality of life for clinical and economic assessment (3). EQ-5D instrument includes 5 items corresponding to the following dimensions: mobility, self-care, usual activities, pain/discomfort, anxiety/depression (Appendix D). Each item can take 1 of 3 responses: (1.) "no problem", (2.) "some problems", and (3.) "severe problems". Overall health status is defined as a 5-digit number and will be converted into a standard utility score ranging between -0.594 (representing severe problems) and 1 (representing no problem): the single index utility score, using a regression model (4) (Appendix E). If response to one or more dimension is missing, the utility score will be missing.

Quality of life parameters include response to each EQ-5D items and change in utility score over time from baseline.

3.1.5.7 Cardiovascular events of interest (other than efficacy endpoints)

Cardiovascular events of interest (other than efficacy endpoints) include clinically significant complications or procedures (not planned at the time of randomization), related to peripheral arterial disease and venous thromboembolic events as listed below:

- Venous thromboembolic events of interest:
 - Deep vein thrombosis (DVT)
 - Pulmonary embolism (PE)
- Lower extremity peripheral arterial disease events of interest:
 - Peripheral lower limb revascularization (endovascular revascularization, surgical revascularization)
 - Critical limb ischemia (including ischemic imputation of lower limb for the event)

The following variables will be analyzed:

- Time from randomization to first occurrence of any other CV events of interest (venous thromboembolic events or lower extremity peripheral arterial disease events)
- Time from randomization to first occurrence of any venous thromboembolic events (DVT or PE)
- Time from randomization to first occurrence of any lower extremity peripheral arterial disease events (peripheral lower limb revascularization or critical limb ischemia)

